Subjects who prematurely discontinue study drug treatment should be encouraged to remain in the study and maintain the same protocol schedule and assessments as described in Table 1. This will allow for continued subject follow-up for key outcome data. Subjects who prematurely

discontinue the study [prior to Day 29 (primary study period)] and are unable to maintain the same protocol schedule should complete early termination (ET) assessments at the time of study discontinuation, as described in Table 1. Nevertheless, all attempts should be made to contact the subject at Day 29 (telephone contact is acceptable) to confirm key study endpoints, including hospitalization and survival.

The primary study period is through Day 29. The end of the study for any individual subject will be defined as the 60-day follow-up contact.

5.7. Prior Therapy, Concomitant Therapy, Permitted Therapy, Cautionary Therapy, and Prohibited Therapy

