3.2.3. Exploratory Endpoints

Efficacy:

- Time to sustained alleviation or improvement of COVID-19 symptoms
- Time to self-reported return to usual (pre-COVID-19) health
- Proportion of subjects requiring post randomization rescue therapy

Note: For subjects randomized into the combination antiviral population, antiviral medications administered post-baseline within 24 hours of first study drug, as part of the combination regimen, are not considered rescue medication.

Note: Rescue therapy for the purpose of the endpoint includes only treatments with direct activity against SARS-CoV-2; and that is administered for COVID-19-related clinical decline.

- Duration and severity of COVID-19 symptom relapse
- Proportion of subjects with both COVID-19 symptom relapse and viral rebound
- Change from baseline in amount of SARS-CoV-2 viral RNA as measured by RT-qPCR overtime
- Time to cessation of SARS-CoV-2 viral shedding by RT-qPCR
- Proportion of subjects negative for SARS-CoV-2 viral RNA by RT-qPCR over time
- Area under the curve (AUC) in the amount of SARS-CoV-2 viral RNA as measured by RT-qPCR
- Potential future biomarker analyses
- Pharmacokinetics: Plasma concentration of AT-511 (free base form of AT-527 [BEM]) and its metabolites

		Intercurrent	Population- Level Summary	Handling of Missing Data Study Withdrawal/ Lost to Follow-
Estimand Primary: difference in the proportion of subjects in the supportive-care population with all-cause hospitalization or death by Day 29 and Day 60, regardless of intercurrent events	Endpoint The proportion of subjects in the supportive-care-only population who are hospitalized for any cause or died due to any cause through Day 29	event handling Treatment-policy strategy approach will be taken. Patients are followed, assessed and analyzed irrespective of their completion of the planned course of the study treatment and irrespective of rescue and concomitant therapy.	for the Variable The common risk difference	Up The outcome measure up to point of study withdrawal will be used

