4.3. Sample Size Considerations

The primary endpoint of proportion of subjects with all-cause hospitalization and all-cause mortality through Day 29 will be compared between treatments using a Cochran-Mantel-Haenszel (CMH) test adjusted for the stratification factors of age and region. The overall type I error will be controlled at a one-sided 0.025 level. Total beta spending was specified at a 0.10 level.

The study was planned to have interim analyses at 30% (futility only) and 65% (futility, safety and efficacy) of the originally planned number of subjects. The interim analyses were removed due to fast enrollment such that the final sample size was reached prior to the first planned interim analysis.

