4.3.1. Sample Size Justifications

Assuming the combined all-cause hospitalization and all-cause mortality rate will be 4% in the placebo arm, the sample size needed to detect a true 60% reduction (corresponding to an absolute difference in rates of 2.4%) in the BEM treatment arm with 90% power at a 1-sided significance

level of 2.5% was determined to be 1982 randomized participants in the supportive-care-only population. Sample size was calculated using SAS (version 9.4) for a 2-sample proportion Chisquare test. Considering the planned interim analyses with both alpha and beta spending according to Lan-Demets approximation of O'Brien Fleming method the sample size should be inflated by a multiplier of 1.055 to a target sample size of 2100 participants (see Section 11.1). Assuming 95% of randomized subjects who receive only supportive care as SOC will meet the mITT-S population criteria (see Section 6.5.4), the study targets total enrollment of 2210 subjects in the supportive-care-only population. If the true rate in the placebo arm is 3%, and assuming a reduction of 60% with BEM, the planned study has at least 80% power to detect a treatment effect. Planned enrollment in the combination arm is up to 300 subjects.

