6.5.6. Completers

Subjects considered as having completed the primary study follow-up are those in the mITT population who were followed through to at least Day 29 or had a hospitalization or death event prior to Day 29. Any subject who has a Day 29 (or subsequent scheduled) visit or an assessment on a date corresponding to study day 29 or later (see Section 6.7.2) will be considered as having been followed through to at least Day 29.

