8.6. Analysis of the Primary Efficacy Endpoint

Table 4:	Summary (of Analyses	Related to the	Primary Effic	cacy Endpoint
	•	•		•/	•

Analysis	Population	Handling of Intercurrent Events	Analysis Approach
Primary Analysis: All- cause hospitalizations and deaths (through Day 29)	mITT-S	Treatment policy	Cochran-Mantel-Haenszel
Supplemental Analysis: All-cause hospitalizations and deaths (through Day 29)	mITT-S Completers	Treatment policy	Cochran-Mantel-Haenszel
Supplemental Analysis: All-cause hospitalizations and deaths (through Day 29)	mITT-S Per-protocol	Treatment policy	Cochran-Mantel-Haenszel
Supplemental Analysis: All cause hospitalizations and deaths (through Day 29)	mITT-S	Intervention with COVID-19 rescue as event (composite handling); Treatment policy otherwise	Cochran-Mantel-Haenszel
Supplemental Analysis: Time to all cause hospitalization and death (through Day 29)	mITT-S	Intervention with COVID-19 rescue as event (composite handling); Treatment policy with censoring for early study discontinuation (prior to Day 29) without event	Kaplan-Meier plot, stratified logrank test

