Intercurrent events are those that occur after treatment initiation and either preclude observation of the variable or affect its interpretation. For the intercurrent events of rescue (e.g., intervention with remdesivir; these will be identified by blinded medical review prior to analysis), a treatment policy approach will be taken, whereby use of rescue and concomitant medications will be ignored, and observations collected after they are administered to the subject will be used. In addition, subjects will be followed, assessed, and analyzed irrespective of their completion of the course of the study treatment. The analysis will be performed based on observed data, and the following measures will be used to reduce missing hospitalization/death data:

- eCRFs capturing clinical information that may be indicative of hospitalization will be reviewed to mitigate the risk of unreported hospitalizations
- study staff may use a public information source to obtain information about survival status if a patient withdraws from the study.

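### SAP Table 2 stops the outcome at study withdrawal, which conflicts with the plan's own provisions for learning of hospitalizations and deaths after withdrawal

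*SAP*

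**What the plan says.** SAP Table 2 has a last column on missing data, headed for study withdrawal and loss to follow-up. The entry is the same in the primary row and all eight secondary rows: "The outcome measure up to point of study withdrawal will be used".

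Other parts of the plan go past that point:

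- Protocol 5.6, for subjects who discontinue the study before Day 29 and cannot keep the visit schedule: "all attempts should be made to contact the subject at Day 29". A telephone call is enough, and the stated purpose is to confirm key endpoints, hospitalization and survival among them.
- SAP 8.6.1, and protocol 8.3.1 in matching terms, analyse the primary endpoint on observed data. Among the measures against missing hospitalization and death data they list: "study staff may use a public information source to obtain information about survival status if a patient withdraws from the study".
- SAP 6.5.6 treats a subject as followed through Day 29 if there is a Day 29 or later visit or "an assessment on a date corresponding to study day 29 or later".
- SAP Table 4, time-to-event row: "Treatment policy with censoring for early study discontinuation (prior to Day 29) without event". No censoring date is given. SAP 8.6.2 adds that the Kaplan-Meier and log-rank analyses take in all data up to Day 29.

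SAP 8.7 applies the primary approach to the secondary endpoints.

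**The concern.** Consider a subject who leaves the study on Day 6, is hospitalized on Day 12, and reports this in the Day 29 call. The event is known, dated and inside the window. Under the literal Table 2 rule the outcome stops at Day 6, so the subject counts as event-free. Under SAP 6.5.6 the same subject could be classed as followed through Day 29, because an assessment exists on that day. A programmer working from the SAP alone would find no mention of the protocol 5.6 contact and no statement of which rule prevails.

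At stake is which events enter the primary endpoint. The design expects few: 42 on placebo and about 17 on BEM in 1050 per arm. The issue is not how to model outcomes that remain unknown. It is whether outcomes already in hand are used.

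**Working it through.** **1. The plan's own figures.** Inputs from SAP 4.3, 4.3.1 and 11.2: "The overall type I error will be controlled at a one-sided 0.025 level"; "Assuming the combined all-cause hospitalization and all-cause mortality rate will be 4% in the placebo arm"; a 60% reduction, so 1.6% on BEM; 90% power; 1:1 allocation. The Pearson formula with pooled variance under the null is

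n = [1.960·√(2·0.028·0.972) + 1.282·√(0.016·0.984 + 0.04·0.96)]² / 0.024² = (0.4573 + 0.2982)² / 0.000576 ≈ 991 per arm,

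or 1982 in total, as stated. Then 1982 × 1.055 = 2091 (stated 2100) and 2100 / 0.95 = 2210.5 (stated 2210). The 95% is the share expected to meet the mITT-S criteria, not a retention rate. No withdrawal rate enters the sample size, so settling the rule leaves it unchanged. SAP 4.3 and 5.1 remove the interim analyses, so power below is for a single test at one-sided 0.025.

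**2. Which rule covers which event.**

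| Event after study withdrawal, onset by Day 29 | Table 2, literal | Other text |
|---|---|---|
| Death found in a public record | not counted | SAP 8.6.1 and protocol 8.3.1 point to using it |
| Death learned at the Day 29 contact | not counted | protocol 5.6 seeks it; 8.6.1 points to using survival status |
| Hospitalization learned at the Day 29 contact | not counted | protocol 5.6 seeks it; no SAP text says it is used |

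The third line is the unprotected one.

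**3. Sensitivity of a close result.** Unstratified Pearson test, n = 1050 per arm, with z = [(b − a)/n] / √[2p(1 − p)/n] and p = (a + b)/2n.

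- 26 v 42: p = 68/2100 = 0.03238; z = 0.015238 / 0.007725 = 1.972; one-sided p = 0.024.
- 26 v 41: p = 67/2100 = 0.03190; z = 0.014286 / 0.007670 = 1.862; one-sided p = 0.031.

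One uncounted placebo event moves the result across 0.025.

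**4. Sensitivity at the design counts.** 17 v 42 gives p = 0.0005. Removing 8 events from each arm (9 v 34) gives p = 0.00006. Removing 8 from placebo alone (17 v 34) gives p = 0.008. The conclusion holds each time.

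**5. Illustration of power.** Assume that a share w of subjects withdraws in each arm, at r times the average event risk, and that all their events fall after withdrawal and go uncounted. With k = w·r, lost events are 42k (placebo) and 16.8k (BEM), and the risk difference is 2.40(1 − k) points. With nothing lost, power at 1050 per arm is 91.6%.

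| w | r | Lost, placebo | Lost, BEM | Risk difference (points) | Power |
|---|---|---|---|---|---|
| 2% | 1 | 0.8 | 0.3 | 2.35 | 91.0% |
| 5% | 1 | 2.1 | 0.8 | 2.28 | 90.1% |
| 5% | 3 | 6.3 | 2.5 | 2.04 | 86.6% |
| 10% | 3 | 12.6 | 5.0 | 1.68 | 79.3% |

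The values of w and r are assumptions; the documents supply neither. The rows are upper bounds for their w and r, since some withdrawn subjects would have had their event before leaving or would never be reached.

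**The case against.** The strongest reply is that the Table 2 column concerns missing data. It can be read as: where later status is unknown, use what was observed and do not impute. That fits SAP 6.8.1 (no imputation) and the observed-data basis in 8.6.1. A hospitalization reported on Day 29 is not missing, so on this reading it counts. The completer definition in 6.5.6 also recognises Day 29 information as follow-up. This stands as a possible reading and may well be the intent. It is not what the column says: the entry names the point of withdrawal, not the last known status, and in the example those are 23 days apart.

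A reader might infer more than the documents support:

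- *That deaths found in public records are dropped.* SAP 8.6.1 lists that source as a way to reduce missing data in this very analysis, which would be pointless if such deaths did not count.
- *That the log-rank analysis censors at the discontinuation date.* Table 4 gives no date, keeps subjects with events, and 8.6.2 includes all data to Day 29. The rule is unspecified, not wrong.
- *That all secondary endpoints in the testing sequence are affected.* Neither collection route informs symptom relapse or viral load rebound, and the Day 29 contact does not supply hospitalizations between Day 29 and Day 60.
- *That the rule contradicts the treatment-policy strategy.* That text covers treatment completion, rescue and concomitant therapy. Study withdrawal is handled in a separate column and is not listed as an intercurrent event.
- *That all-cause death is especially fragile.* With 0 v 4 deaths Pearson gives p = 0.023, but with expected counts of 2 per arm the approximation is poor, and one-sided Fisher gives 0.062. SAP 8.2 itself warns about small cells.

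**Conclusion.** The finding is an unresolved conflict over which events count. Table 2, taken literally, excludes outcomes that protocol 5.6 sets out to collect and that SAP 8.6.1 partly relies on. The clear gap is a hospitalization after study withdrawal that is learned at the Day 29 contact: it belongs to the primary endpoint and no SAP text secures it.

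It would be too strong to say that the plan definitely discards known events, or that the treatment comparison is biased. How many subjects withdraw, are later reached and have had an event is not stated, and nothing shows that this would differ by arm. A loss from both arms need not hurt: from 26 v 42, removing one event in each arm (25 v 41) gives p = 0.023, still below 0.025. The effect is negligible at the design counts and can decide the test only near the boundary, as with 26 v 42 against 26 v 41. The plan should still be corrected. The rule bears on the primary endpoint, the change costs almost nothing, and SAP section 2 says the plan is to be final before unblinding.

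**What to change.** In the last column of SAP Table 2, for the rows built on hospitalization, death or medically attended visits, replace the entry with wording to this effect: all events with onset through Day 29 (or Day 60, where that is the time point) are counted whatever their source and whether or not the subject had withdrawn from the study, including the protocol 5.6 Day 29 contact, SAE reports and public survival records; only subjects whose later status is unknown are analysed on data up to last contact.

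In the Table 4 time-to-event row, state that subjects without an event are censored at the date last known to be event-free, including a Day 29 contact. This agrees with 8.6.2.

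The cost is SAP wording and one derivation rule. The contacts and record checks are already planned, so no new data are needed, and the sample size does not change. One small downside is that hospitalizations learned by telephone may be less well documented.

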4. STUDY DESIGN

4.1. Summary of Study Design

AT-03A-017 is a Phase 3 randomized, double-blind, placebo-controlled study, conducted in non-hospitalized adult subjects (\geq 18 years of age) with mild or moderate COVID-19.

Age and comorbidities will determine a patient's risk and eligibility. Onset of COVID-19 symptoms will have occurred ≤ 5 days before randomization.

BEM 550 mg or matching placebo will be administered BID for 5 days (10 doses, with each dose including 2 tablets).

Locally available standard of care (SOC) treatment is to be initiated in parallel with study drug (add-on). SOC treatments with direct antiviral activity against SARS-CoV-2 are allowed, but are to be initiated during screening and/or within 24 hours prior to or after randomization.

Subjects will be randomized 1:1 (active:placebo) to one of the following arms:

- 550 mg BEM (2 x 275 mg tablets) BID for 5 days
- Placebo (2 tablets) BID for 5 days

Randomization will be stratified by geographic region (North America, Europe, Asia, and rest of world [ROW]), age (< 65 years old vs \geq 65 years old) and by the type of SOC which the investigator plans to administer in parallel at time of study drug initiation. The type of SOC received will be used to classify subjects into two categories:

- Combination antiviral stratum (subsequently referred to as the combination antiviral population): In addition to study drug, the subject will be initiated on a local SOC regimen which includes a treatment with direct SARS-CoV-2 antiviral activity. Examples include nirmatrelvir/ritonavir, molnupiravir, favipiravir, mAbs
- Supportive-care-only stratum (subsequently referred to as the supportive-care-only population): the SOC regimen the subject will receive does not include any treatment with direct SARS-CoV-2 antiviral activity

Although randomization is stratified by whether COVID-19 drugs with antiviral effects are administered, both strata allow local SOC therapies without direct antiviral effects (i.e., corticosteroids).

Patients who require SOC treatment with a non-compatible antiviral treatment, defined as those with a potential drug-drug interaction (DDI) with BEM (e.g., remdesivir), are excluded.

For subjects who deteriorate on study, any rescue therapy which is SOC for progression to severe COVID-19 is permitted. If rescue therapy will be remdesivir, study drug will be discontinued before initiation of remdesivir.

Overall, up to 2510 eligible subjects with COVID-19 will be enrolled, with a target of 2210 subjects in the supportive-care-only population and 300 subjects in the combination antiviral population. The primary study endpoint (hospitalization/death) will be evaluated in the supportive-care-only population.

The primary study period is up to 30 days, including up to 1 day for screening and 29 days following randomization. Extended follow-up data will be collected through Day 60 for

Version 5 June 24, 2024

mortality and medically attended visit (MAV) assessment. The Day 60 follow-up contact marks the end of study participation for each subject and the study ends when the last subject completes the Day 60 follow-up contact.

A schematic of the study design is presented in Figure 1.

Figure 1: Study Design

4.2. Definition of Study Drugs

Study drug (550 mg BEM or matching placebo) is to be administered twice daily for 5 days, i.e., a total of 10 doses (20 tablets total). Each dose will be taken as 2 tablets (2x 275 mg BEM tablets or 2 matching placebo tablets).

4.3. Sample Size Considerations

The primary endpoint of proportion of subjects with all-cause hospitalization and all-cause mortality through Day 29 will be compared between treatments using a Cochran-Mantel-Haenszel (CMH) test adjusted for the stratification factors of age and region. The overall type I error will be controlled at a one-sided 0.025 level. Total beta spending was specified at a 0.10 level.

The study was planned to have interim analyses at 30% (futility only) and 65% (futility, safety and efficacy) of the originally planned number of subjects. The interim analyses were removed due to fast enrollment such that the final sample size was reached prior to the first planned interim analysis.

4.3.1. Sample Size Justifications

Assuming the combined all-cause hospitalization and all-cause mortality rate will be 4% in the placebo arm, the sample size needed to detect a true 60% reduction (corresponding to an absolute difference in rates of 2.4%) in the BEM treatment arm with 90% power at a 1-sided significance

level of 2.5% was determined to be 1982 randomized participants in the supportive-care-only population. Sample size was calculated using SAS (version 9.4) for a 2-sample proportion Chisquare test. Considering the planned interim analyses with both alpha and beta spending according to Lan-Demets approximation of O'Brien Fleming method the sample size should be inflated by a multiplier of 1.055 to a target sample size of 2100 participants (see Section 11.1). Assuming 95% of randomized subjects who receive only supportive care as SOC will meet the mITT-S population criteria (see Section 6.5.4), the study targets total enrollment of 2210 subjects in the supportive-care-only population. If the true rate in the placebo arm is 3%, and assuming a reduction of 60% with BEM, the planned study has at least 80% power to detect a treatment effect. Planned enrollment in the combination arm is up to 300 subjects.

4.4. Randomization

Subjects will be randomized 1:1 (active:placebo) to one of the following arms:

- 550 mg BEM (2 x 275 mg tablets) BID for 5 days
- Placebo (2 tablets) BID for 5 days

Randomization will be stratified by geographic region (North America, Europe, Asia, and ROW), age (< 65 years old, \geq 65 years old) and by the type of SOC which the investigator plans to administer in parallel at time of study drug initiation. The primary stratification factor is the type of background SOC that the investigator plans to administer as this determines whether the subject is in the supportive-care only group (i.e. may be included in the primary analysis population) or the combination antiviral group. Within each of the primary strata, randomization is further stratified by geographic region (North America, Europe, Asia, and ROW) and age (<65 and \geq 65).

The type of SOC received will be used to classify subjects into two categories:

- Combination antiviral stratum (subsequently referred to as the combination antiviral population):In addition to study drug, the subject will be initiated on a local SOC regimen which includes a treatment with direct SARS-CoV-2 antiviral activity. Examples include nirmatrelvir/ritonavir, molnupiravir, favipiravir, mAbs
- Supportive-care-only stratum (subsequently referred to as the supportive-care-only population): the SOC regimen the subject will receive does not include any treatment with direct SARS-CoV-2 antiviral activity

4.5. Clinical Assessments

The following assessments will be performed at Screening, defined as within 24 hours of first dose of study drug, only:

- Demographics
- Medical history and baseline characteristics
- Pre-existing symptoms
- Height and weight
- Complete physical examination

)

- Pregnancy test (females of childbearing potential)
- Rapid test for influenza.

Information on study drug dosing will be collected on Days 1-6 and a plasma sample for evaluation of sparse pharmacokinetics will be collected on Day 5.

The following assessments will be performed at visits corresponding to Days 1, 5, 14 and Early Termination (ET):

- Central safety laboratory values
- Potential blood biomarkers

The following assessments will be collected at each study visit from Day 1 onward (during the 29-day follow-up period i.e., Days 1, 3, 5, 7, 14, 29, and ET if applicable) with exceptions noted:

- Vital signs, to Day 14
- Symptom-targeted physical examination, as clinically indicated
- Nasopharyngeal (NP) swab for central assessment of SARS-CoV-2 virus (quantitative RT-PCR and potential viral titer)
- Adverse events (SAEs out to Day 60)
- Concomitant medications
- Assessment of COVID-19 related medically attended visit(s) (out to Day 60).

Patient reported COVID-19 symptoms will be collected daily on Days 1-29. Symptoms are captured via the COVID-19 symptom diary (see Section 11.1).

At the extended follow-up visit on Day 60, planned collection includes assessment of medically attended visit(s) and serious adverse events.

Version 5 June 24, 2024

